Eligible patients will be screened and identified by research assistants of this study. Upon agreeing to participate in the study and signing of the informed consent, the patients will be randomised to either the control or intervention group using a random number generator or an equivalent by the research assistants.

Patients randomly assigned to the usual or conventional care arm may be subject to as needed referral to the nurses for soft skill-related DM counselling and dietitian for diet control, at the discretion of the physician. These patients may be seen by different physicians at each visit, and pharmacists will not be involved in drug optimization except for dispensing.

Patients randomly assigned to the collaborative care arm will see a healthcare team comprising clinical pharmacists in addition to physicians, nurses and dietitians. The clinical interventions carried out by the clinical pharmacist include but are not limited to counselling patients about drug therapy, performing simple physical assessments, ordering pertinent follow-up visits and laboratory tests on behalf of the physicians, and initiating, titrating, and terminating medications per the NHG Hypertension, Diabetes, Lipids Clinic (HDL-C) Protocol and under the supervision of the physicians as appropriate. The supervision is usually in the endorsement of prescriptions prepared by clinical pharmacists. In addition, the clinical pharmacist will serve as a bridge between patients and physicians to increase communication, and patients will need to be seen by physicians at least every four months. As needed, referrals to nurses and dieticians will also be actively made by the clinical pharmacist and vice versa. The clinical pharmacist will schedule clinic appointments approximately every four to six weeks in the 12-month interventional period. If the patient's DM is well-controlled, i.e. with stable improvements in clinical measures, the clinical pharmacist may replace one or two clinic visits with telephone counselling at his/her discretion. All clinical pharmacists are board-certified pharmacotherapy specialists and/or board-certified ambulatory care pharmacist, and they have undergone the 3-month internal rotational endocrinology training held at Tan Tock Seng Hospital, comprising preceptors who are endocrinologists, senior clinical pharmacists, diabetes nurse educators, dietitian, and podiatrist, similar to the previous study conducted.¹⁸

Data Collection:

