The economic evaluation will be conducted from an institutional perspective. Direct healthcare costs will be estimated over 12 months. The direct costs will include physicians' consultation fees, laboratory and procedures, medication costs, DM-related hospitalization, and DM-related A&E visits.

Number of Subjects to be enrolled:

A 12-month study conducted in the United States of America involving the collaborative care model reported an effect size of 0.4.²⁰ With an allocation ratio of 1:1 into the intervention or control arms, approximately 125 patients are needed in each arm, to obtain a statistical power of 80% (two-sided Type I error rate = 0.05) and after taking into account a 20% dropout rate. As such, 250 patients will be needed to assess the effectiveness of a collaborative care model versus the usual model of care in the polyclinics.

Data source:

Clinical data will be collected from patient electronic case notes, prescription records accessed from CPSS2 and iPharm and investigation results from the electronic laboratory module in CPSS2. Humanistic data and incidence of hypoglycaemia will be elucidated through participant's self-reported questionnaires. Cost data will be obtained from the respective institution financial databases.

Data Analysis:

Descriptive analyses will be performed on all variables. The differences in the improvement of clinical and patient-reported outcomes will be examined between the two groups using the Student's t test or Wilcoxon rank-sum test as appropriate. Categorical data between the two study groups will be analyzed using the Chi-square test for independence or Fisher's exact test when expected cell size is less than 5. Pearson's product-moment correlation will be used to examine correlations between continuous variables such as HbA1c and HRQoL scores. Baseline factors that are significant in the bivariate analysis will be included in a multiple linear regression model to investigate the unique impact of the intervention on and the unique association of individual factors with each outcome score while adjusting for other covariates. The level of Type I error rate will be set at P < 0.05.

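### The direct-cost list prices physician consultations but not the clinical pharmacist contacts that only the collaborative arm receives, so costing by the list favours that arm

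*Protocol*

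**What the plan says.** The Economic Outcomes section sets the viewpoint: "The economic evaluation will be conducted from an institutional perspective". It then gives the only list of cost components in the Protocol: "The direct costs will include physicians' consultation fees, laboratory and procedures, medication costs, DM-related hospitalization, and DM-related A&E visits". Table 3 says only that direct costs will be measured, and the Data source section names the institutions' financial databases without listing items.

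The Procedures section describes what differs between the arms.

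- **Collaborative arm, pharmacist:** "The clinical pharmacist will schedule clinic appointments approximately every four to six weeks in the 12-month interventional period". In well-controlled patients the pharmacist "may replace one or two clinic visits with telephone counselling".
- **Collaborative arm, physician:** "patients will need to be seen by physicians at least every four months".
- **Usual care, pharmacist:** "pharmacists will not be involved in drug optimization except for dispensing".
- **Nurses and dietitians:** usual-care patients "may be subject to as needed referral to the nurses for soft skill-related DM counselling and dietitian for diet control". For the collaborative arm, "As needed, referrals to nurses and dieticians will also be actively made by the clinical pharmacist and vice versa".

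The Clinical Outcomes section counts diabetes-related clinic visits separately for physicians, pharmacists, nurses and dietitians, but as a clinical outcome. Nothing in the Protocol carries the pharmacist visits into the costs.

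**The concern.** The list names one profession's consultations, the physician's, and omits the profession whose involvement defines the intervention. Pharmacist time is a cost to the institution, so under the stated perspective it belongs in the total. The omission does not cancel between arms, because usual-care patients have no such appointments.

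The costs feed three analyses in the Data Analysis section: the Wilcoxon rank-sum test on summed costs, the gamma model with log link, and the numerator of the incremental cost-effectiveness ratio. Economic outcomes are also part of the central hypothesis under Specific Aims and Objectives. If pharmacist contacts go uncosted, the collaborative arm can appear cheaper because its main input was left out.

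Substitution could make this worse. The Procedures let pharmacists order follow-up visits and tests on the physicians' behalf and adjust medication. If pharmacist contacts replace some physician visits, the list credits the saved physician fee without charging for the replacement. The Protocol does not give physician visit frequency in usual care, so this remains a possibility only.

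**Working it through.** The Protocol gives no contact count, unit cost or cost difference on this point, so there is no stated figure to reproduce. The check derives the contacts from the schedule and then traces the effect of omitting them.

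**Inputs from the Protocol (Procedures)**

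- Pharmacist appointment interval in the collaborative arm: 4 to 6 weeks, over 12 months (52 weeks).
- Physician visits in the collaborative arm: at least one every 4 months.
- Pharmacist appointments in usual care: none; dispensing only.

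**Scheduled contacts per collaborative-arm patient**

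- Pharmacist, every 6 weeks: 52 / 6 = 8.67.
- Pharmacist, every 4 weeks: 52 / 4 = 13.
- Physician, minimum: 12 / 4 = 3.

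Replacing one or two clinic visits by telephone does not change these totals, since a telephone session is still a pharmacist contact.

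**Pharmacist share of physician-plus-pharmacist contacts, at full attendance and minimum physician frequency**

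- 8.67 / (8.67 + 3) = 74.3%.
- 13 / (13 + 3) = 81.3%.

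**Range under assumptions.** The Protocol gives neither attendance nor actual physician frequency. I assume 50% to 100% attendance at pharmacist appointments and 3 to 6 physician visits a year.

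| Attendance | k (pharmacist contacts) | Share with 3 physician visits | Share with 6 physician visits |
|---|---|---|---|
| 100% | 8.67 to 13 | 74.3% to 81.3% | 59.1% to 68.4% |
| 50% | 4.33 to 6.5 | 59.1% to 68.4% | 41.9% to 52.0% |

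So k lies between 4.3 and 13, and the share between 42% and 81%. These are shares of contacts within one arm. They are not shares of cost and do not measure the bias.

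**Effect on the cost comparison.** Let c be the unit cost of a pharmacist contact and D the collaborative-minus-usual difference in mean cost on the listed items.

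- Understatement per patient: k × c in the collaborative arm, 0 in usual care.
- Difference with pharmacist contacts included: D + k × c. If D is a saving smaller than k × c, its sign reverses, leaving aside any between-arm difference in nurse and dietitian contacts.
- Wilcoxon test: the collaborative cost distribution is shifted downwards relative to usual care.
- Gamma model with log link: the collaborative-to-usual ratio of mean costs is too low.
- Cost-effectiveness ratio: with E the difference in HbA1c reduction, and E positive, the ratio is too low by k × c / E.

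At full attendance, with E assumed at 0.3, 0.5 or 0.8 percentage points, the shift in the ratio is:

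- E = 0.3: 8.67c / 0.3 = 28.9c to 13c / 0.3 = 43.3c.
- E = 0.5: 8.67c / 0.5 = 17.3c to 13c / 0.5 = 26c.
- E = 0.8: 8.67c / 0.8 = 10.8c to 13c / 0.8 = 16.3c.

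Each is per percentage point of HbA1c. The Protocol gives no value for c, so these cannot be turned into money.

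**The case against.** The strongest reply is that the sentence says what direct costs will include and does not say the list is complete. The institutional perspective, the use of institutional financial databases and the reference in Data Analysis to total costs all fit a broader costing. A full schedule of resources and unit costs may properly sit in a later analysis plan, and clinic visits by profession are already counted, so the pharmacist visits could be costed without new data.

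This stands in part. It makes the finding conditional: the bias arises if costs are built from the list as written. It does not remove the defect, because the Protocol did not defer the matter. It set out components and named physicians alone, although Clinical Outcomes names all four professions when counting visits. Listing consultations separately from procedures also makes it hard to read a pharmacist consultation into the procedures item. The planned sensitivity analysis would not repair the gap, since it varies the variables and assumptions used in the analysis, and an omitted cost is not among them.

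A second reply is that, without a unit cost, k × c could be small beside medication and hospitalization costs. That is correct: the direction of the pharmacist component is known and its size is not.

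A third is that nurse and dietitian contacts are also unlisted. Both arms may receive them as needed, and the Protocol does not settle which arm would have more. The net effect of costing all three professions is therefore open; only the pharmacist component has a known direction.

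**Conclusion.** The concern holds. Costing by the list as written leaves out a cost that only the collaborative arm incurs, and that component biases all three economic analyses towards collaborative care. The understatement is k × c per collaborative-arm patient and zero in usual care, with k up to about 8.7 to 13 at full attendance, or 4.3 to 13 if attendance is 50% to 100%. The monetary size cannot be determined from the Protocol.

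The conclusion rests on three conditions: costs follow the stated list, the statement about direction concerns the pharmacist component alone, and the effect on the cost-effectiveness ratio assumes a positive difference in HbA1c reduction. Clinical and humanistic results are not touched. It should be fixed before the economic analysis.

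**What to change.** In the direct-cost sentence under Economic Outcomes, insert one item after the physician fees: the cost of clinical pharmacist, nurse and dietitian contacts in both arms, covering clinic and any telephone sessions. Leave the other items as they are.

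- **Quantities:** take clinic contacts from the visit counts by profession under Clinical Outcomes. Take telephone sessions from the case notes where appointment cards do not show them, after checking that the notes record them.
- **Unit costs:** take them from the institutional financial databases. If these hold no unit cost for a profession, state how one is derived and vary it in the sensitivity analysis already planned.

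The cost is one sentence of Protocol wording and a small costing task: unit costs for three more professions and a search for telephone sessions. No new visits are needed, and it can be done before the economic analysis. The drawbacks are that a pharmacist unit cost may have to be derived, and that the pharmacist component will make the cost-effectiveness ratio less favourable to collaborative care if the difference in HbA1c reduction is positive.

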The main clinical parameters to be collected include HbA1c, SBP, total cholesterol, LDL, HDL, and TG. These short-term surrogate markers are predictive of the development of long-term DM-related complications. In addition, total cholesterol and other lipid parameters allow for estimation of cardiovascular risk. While several laboratory measures of glycemic levels are available, HbA1c will be used in this study as it is a recommended and reliable index of mean glycemic control over three months. Other outcome measures include: 1) incidence of minor and major hypoglycemia reported by patients, 2) frequency of DM-related clinic visits (by physician, pharmacist, nurses, dietitians) as indicated on patients' appointment card and hospitalizations. Minor hypoglycemic events are defined as blood glucose of < 4.0 mmol/L or signs and symptoms with known precipitating causes such as irregular eating habits, increased daily activity or other attributes that can be modified. The minor hypoglycemic event should allow the patient to recover quickly with or without the ingestion of fast-acting glucose. Major hypoglycemic events are defined as any hypoglycemic symptoms, regardless of frequency, which require help from another person. The clinical information and laboratory values will be collected from the clinical databases available at the study sites, patient case notes, and patient self-reported questionnaires at baseline, at 6- and 12-month during the study period. Baseline laboratory values will be collected at enrolment. If values are not available at enrolment, the most recent value available within the 6 months preceding enrolment will be recorded.

Humanistic Outcomes

Health-related quality of life (HRQoL) will be assessed using Research Assistant-administered questionnaires at baseline and as close to the 6-month and 12-month follow-ups as possible. The HRQoL measures will include a generic measure, EQ-5D-5L, and a DM-specific measure, the Audit of Diabetes Dependent Quality of Life (ADDQoL), and Problem Areas in Diabetes (PAID). Self-care management capabilities of patients will be assessed by the Summary of Diabetes Self-Care Activities Measure (SDSCA).

Economic Outcomes

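### The named test of improvement does not by itself use patients who have only baseline and month-6 values, so the 12-month comparison is exposed to bias if dropout depends on interim control differently by arm

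*Protocol*

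**What the plan says.** All references are to the protocol.

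- **Data Analysis, main comparison:** "The differences in the improvement of clinical and patient-reported outcomes will be examined between the two groups using the Student's t test", with a Wilcoxon rank-sum test as the alternative. The sentence names no time point.
- **Data Analysis, adjusted comparison:** "Baseline factors that are significant in the bivariate analysis will be included in a multiple linear regression model". This conditions on baseline only.
- **Number of Subjects to be enrolled:** the calculation starts from one earlier trial: "A 12-month study conducted in the United States of America involving the collaborative care model reported an effect size of 0.4". From this, "approximately 125 patients are needed in each arm", a figure reached "after taking into account a 20% dropout rate".
- **Clinical Outcomes:** values come from site databases, case notes and "patient self-reported questionnaires at baseline, at 6- and 12-month during the study period". Month-6 values are therefore planned.
- **Data source:** laboratory and clinical values are taken from electronic records. Humanistic outcomes and hypoglycaemia rest on what participants report.
- **Cost-effectiveness analysis:** effectiveness is the fall in HbA1c from baseline to month 12. This is the one place where an analysis is tied to month 12.

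**The concern.** The study is designed to run for 12 months, and its background notes that in Singapore the care model has been evaluated prospectively for only 6. The 12-month contrast is therefore the one that matters most. The HbA1c difference over the same period is also the denominator of the cost-effectiveness ratio.

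A two-sample test of change to month 12, or a regression of it on baseline factors, needs a month-12 value from each patient. Someone seen at month 6 and lost afterwards adds nothing to it, although the month-6 value predicts the missing one. Testing month-6 improvement separately would use that value, but not for the 12-month contrast.

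Loss that is related to outcome and differs by arm is plausible. Under Procedures, collaborative-care patients have pharmacist appointments about every four to six weeks, some replaceable by telephone when control is good. Usual-care patients have no comparable schedule. Contact therefore differs by arm and, in one arm, depends on interim control. If staying in the study does too, completers are selected differently in the two arms and their difference is not the randomised effect.

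**Working it through.** **1. The plan's own figure.** Inputs: effect size 0.4, 80% power, two-sided 0.05, 1:1 allocation, 20% dropout.

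- Normal approximation: n = 2(1.960 + 0.842)² / 0.4² = 98.1, so 99 per arm.
- The exact t-test calculation gives 99.08, so 100 per arm.
- 100 / (1 − 0.20) = 125 per arm.

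The stated figure reproduces. Power is about 80.7% with 100 per arm and 88.5% if all 125 contributed, so the inflation treats dropouts as giving the test no information. That fits a completer analysis.

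**2. What completers estimate.** Assumptions, not in the protocol:

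- true effect of 0.40 SD at months 6 and 12;
- correlation ρ of 0.5 to 0.7 between month-6 and month-12 change;
- 20% leaving, all after month 6, with the log-odds of leaving linear in standardised month-6 change.

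In each arm the completer mean at month 12 equals the true mean + ρ·m, where m is the mean standardised month-6 deviation of those who stay. When the poorly controlled leave and 20% go, m = −0.096, −0.173 and −0.262 for log-odds of 0.5, 1 and 2 per SD. The estimated effect is then:

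- 0.40 + ρm if this happens in usual care only;
- 0.40 − ρm if in collaborative care only;
- 0.40 + 2ρm if the poorly controlled leave usual care and the well controlled leave collaborative care;
- 0.40 + ρ(m₀ − m₁) if one rule on the month-6 value applies in both arms, with 20% leaving overall. Here (m₀, m₁) = (−0.103, −0.089), (−0.195, −0.151) and (−0.309, −0.214).

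Results (truth 0.40; each cell runs from ρ = 0.5 to ρ = 0.7):

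| Dropout pattern | log-odds 0.5 | 1 | 2 |
|---|---|---|---|
| Unrelated to month 6 | 0.40 | 0.40 | 0.40 |
| Same rule in both arms | 0.39 to 0.39 | 0.38 to 0.37 | 0.35 to 0.33 |
| Usual care only | 0.35 to 0.33 | 0.31 to 0.28 | 0.27 to 0.22 |
| Collaborative care only | 0.45 to 0.47 | 0.49 to 0.52 | 0.53 to 0.58 |
| Opposite directions | 0.30 to 0.27 | 0.23 to 0.16 | 0.14 to 0.03 |

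Simulation with 2 million patients per arm agrees to about 0.01. An estimator using every month-6 value returned 0.397 to 0.403 throughout.

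**3. On an HbA1c scale.** Table 1 gives −1.7 and −0.9 for the study cited for the effect size. If the 0.4 refers to that outcome, which the protocol does not say, SD = 0.8 / 0.4 = 2.0. A separate simulation (SD 2.0, truth 0.80, about 19-23% dropout) gave:

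- opposite directions by arm: 0.55 to 0.72;
- one arm only: 0.69 to 0.76, or 0.84 to 0.91, depending on the arm;
- random, or the same rule relative to each arm's own mean: about 0.80;
- an estimator using month 6: 0.79 to 0.81.

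These correspond to mild dependence. At log-odds 0.3 (m = −0.059, ρ = 0.5) to 0.5 (m = −0.096, ρ = 0.7), the formulas give 2.0 × (0.40 + 2ρm) = 0.68 to 0.53 for opposite directions, and 2.0 × (0.40 ± ρm) = 0.74 to 0.67 or 0.86 to 0.93 for one arm. Stronger dependence widens the range, as the table shows.

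**4. Power.** With 100 completers per arm, power ≈ Φ(d√50 − 1.96). For d = 0.40, 0.39, 0.33 and 0.28 this gives 81%, 79%, 65% and 51%.

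**The case against.** **The protocol does not say that dropouts are discarded.** A reader might infer it from the choice of test, but there is no completer set, exclusion rule or missing-data rule. A t test can be run on imputed data, and such rules commonly sit in a statistical analysis plan, which is not shown here. This stands: the missing rule is no finding. What remains is that the methods actually named do not by themselves use the month-6 data for the 12-month contrast.

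**Month 12 is not in the test sentence.** Also true. It is inferred from the 12-month design and the cost-effectiveness definition, and month-6 improvement could be tested under the same sentence. Month-6 values are unused in one comparison, not lost altogether.

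**HbA1c is among the outcomes least at risk.** HbA1c, blood pressure and lipids come from clinic records, and nothing ends extraction when a patient stops study contact. The HbA1c-scale figures illustrate the mechanism; they do not forecast bias in that outcome. Questionnaire outcomes have no such back-up.

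**The bias figures rest on chosen patterns.** They do. The sign can go either way. With no treatment effect and one dropout rule in both arms, selection cancels, so that pattern creates no false positive. The month-6 estimator performs well partly because the scenarios are missing at random with month 6 always observed.

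**A likelihood model would displace the rank-sum option for non-normal data.** This is fair, and it is met by multiple imputation with the rank-sum test kept.

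**Conclusion.** The concern holds in limited form. The protocol expects 20% dropout, sizes the trial as if dropouts contribute nothing, and names tests that by themselves leave month-6 values out of the 12-month contrast. A better method is available from data already planned.

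The size of any bias is conditional. With arm-specific dependence of mild strength, the completer estimate ran from 0.55 to 0.91 against a true 0.80. It was unbiased under random dropout. Under one rule in both arms it was 2-17% too small, with the upper end needing the strongest dependence assumed. The correlations, dropout patterns and SD are all assumptions.

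Three stronger conclusions are tempting and unsupported: that the plan discards dropouts, that the HbA1c result will be biased, and that the sample size is wrong. The first is not stated anywhere, the second ignores the record-based data source, and 125 per arm reproduces.

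**What to change.** In Data Analysis:

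- Make the main analysis of continuous outcomes a longitudinal likelihood model with baseline, month 6 and month 12, arm-by-visit terms and unstructured covariance.
- Where the rank-sum test is kept for a non-normal outcome, use multiple imputation that includes the month-6 value.
- Analyse all randomised patients as allocated, with the month-12 contrast as the treatment effect.
- Keep the t or rank-sum test as a supportive analysis.

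As a clarification in Clinical Outcomes, state that record-based values are extracted to month 12 for everyone, including those who stop visits or questionnaires, unless consent for record access is withdrawn.

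The cost is a change of wording and a slightly more complex analysis, with no extra patients or visits and no change to the 125 per arm. The method relies on missing at random. It does not help for dropout before month 6, or for dropout driven by later values that are never observed, and the plan should say so.

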The purpose of this study is to determine the effectiveness of the collaborative care model in Singapore in which clinical pharmacists, nurses and dietitians are active participants who collaborate with physicians in caring for patients with type 2 DM. Since type 2 DM is a cardiovascular risk equivalent, co-morbidities such as hypertension (HTN) and dyslipidaemia (DLP) will also be evaluated to assess the holistic care provided for our patients afflicted with these top chronic diseases in Singapore.

Specifically, this study aims to evaluate the long-term effectiveness and sustainability of an integrated collaborative care model comprising of a healthcare team (physician, clinical pharmacist, nurse, and/or dietitian) compared to the usual or conventional healthcare model (physician-centred care) mainly in the following outcomes (Table 2).

Types of Outcomes	Descriptions				
Clinical	• Glycated haemoglobin (HbA1c), systolic blood pressure (SBP), low density				
	lipoprotein (LDL), total cholesterol, high density lipoprotein (HDL) and fasting				
	triglyceride (TG) levels				
	 Incidence of minor and major hypoglycaemia 				
	 DM-related clinical visit and hospitalization 				
Humanistic	Health-related quality of life				
	Self-care management				
	Diabetes-related distress				
Economic	Cost effectiveness				
	Productivity				

Table 2. Outcome Measures for Proposed Study

The central hypothesis of this study is that patients with type 2 DM under the collaborative care model will have greater improvements in the clinical, humanistic and economic outcomes assessed than those under conventional care.

Data collection period:

12 March 2018 to 12 March 2020

Study Design and Methodology:

Study Design and Setting

This proposed project is a prospective, randomized controlled study to be conducted over a 12month period. This multi-centre study will be conducted in Bukit Batok and Choa Chu [name] Polyclinics.

Study Participants

Patients aged \geq 21 years with Type 2 DM (HbA1c > 7%) and polypharmacy (\geq 5 medications) will be eligible for this study. Patients with Type 1 DM or who are unable to communicate independently in English, Chinese or Malay will be excluded from this study.

Procedures

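### The tests named for hypoglycaemia and for DM-related visits and hospitalisation take no account of follow-up time, and for visits and hospitalisation an improvement from baseline cannot be formed

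*Protocol*

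**What the plan says.** Table 2 lists "Incidence of minor and major hypoglycaemia" and DM-related visits and hospitalisation among the clinical outcomes. The Clinical Outcomes section places both under other outcome measures, apart from the main parameters (HbA1c, SBP and lipids), and describes visits as a frequency. Hypoglycaemia comes from patient questionnaires at baseline, 6 and 12 months. Table 3 marks a baseline for hypoglycaemia and a dash at baseline for visits and hospitalisation.

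The Data Analysis section states: "The differences in the improvement of clinical and patient-reported outcomes will be examined between the two groups using the Student's t test", with the Wilcoxon rank-sum test as the alternative. For categories it states: "Categorical data between the two study groups will be analyzed using the Chi-square test for independence or Fisher's exact test". Adjusted analyses use multiple linear regression. The only model for skewed data, a log-link gamma model, is reserved for costs. No count or rate method and no allowance for time at risk is named, and the text does not say which listed test applies to which event outcome.

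The sample size section plans for 20% dropout.

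**The concern.** These outcomes are events that can recur in one patient. Counts of this kind are usually skewed with many zeros, and patients who leave early have less time in which to report an event. Three problems follow.

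- No listed test uses the length of follow-up.
- If the outcome is reduced to any event or none, a patient with ten events counts the same as a patient with one.
- The stated target, a difference in improvement, does not exist for visits and hospitalisation, because nothing is collected at baseline to improve from.

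The Procedures section has clinical pharmacists initiating and titrating medication in the collaborative arm, so a rise in hypoglycaemia is a result the trial would want to be able to see. A weak test makes an uninformative finding of no difference more likely.

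**Working it through.** **The plan's own figure.** The inputs are "reported an effect size of 0.4", "to obtain a statistical power of 80" per cent, "two-sided Type I error rate = 0.05" and "With an allocation ratio of 1:1 into the intervention or control arms". Then n = 2(1.96 + 0.84)²/0.4² ≈ 98, or 99 per arm with the t correction, and 99/0.8 = 123.75, so 124. The protocol says "approximately 125 patients are needed in each arm", which agrees. This sizing is for a standardised mean difference and gives no assurance about event outcomes.

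**Assumptions.** The documents give no event rate, dispersion or dropout by arm. Assumed here:

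- control rates of 0.3, 1 and 3 events per patient-year, and a rate ratio of 1.6;
- gamma-Poisson counts with dispersion 1;
- 125 per arm, with 20% dropout in each arm;
- data only from completed questionnaires: 12 months for completers, 6 months if lost after month 6, nothing if lost earlier;
- the same underlying patient rate before and after enrolment, apart from treatment.

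**Why any/none is weak.** With dispersion 1, the chance of at least one event in a year at rate μ is μ/(1 + μ).

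| Control rate | Control, any event | Intervention, any event | Difference |
|---|---|---|---|
| 0.3 | 0.3/1.3 = 23.1% | 0.48/1.48 = 32.4% | 9.4 points |
| 1 | 1/2 = 50.0% | 1.6/2.6 = 61.5% | 11.5 points |
| 3 | 3/4 = 75.0% | 4.8/5.8 = 82.8% | 7.8 points |

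From 1 to 3 events per year the difference in mean counts triples (0.6 to 1.8), but the any/none difference shrinks. By the normal approximation with 125 per arm and no dropout, the power at μ = 1 is Φ(0.1154/0.0628 − 1.96) = Φ(−0.12) ≈ 45%. Simulation without dropout also gives 45%.

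**Simulated power, 20% dropout in each arm, questionnaire schedule.**

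| Analysis | 0.3 per year | 1 per year | 3 per year |
|---|---|---|---|
| Chi-square, any/none | 32% | 41% | 31% |
| Rank-sum on counts | 35% | 58% | 71% |
| t test on counts | 40% | 68% | 84% |
| t test on change | 24% | 63% | 98% |
| Rate model, time offset, baseline count | 45% | 81% | 99% |

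Under no true difference the rate model rejected in 5–7% of runs. A separate simulation on the same schedule agreed with the table to within a few points.

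**What drives the gain.** With equal dropout and no baseline term, a t test on counts nearly matches the rate model. With dropout times uniform over the year and events counted up to dropout, power was 42%, 74% and 86% against 43%, 75% and 88%. On the questionnaire schedule at 1 event per year it was 71% against 73%. So, when dropout is equal, the advantage over a t test on counts comes mostly from baseline adjustment.

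**Unequal dropout.** With 10% against 30%, more in the higher-rate arm, power on the questionnaire schedule was as follows.

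| Rate | Chi-square | Rank-sum on counts | t on counts | Unadjusted rate model |
|---|---|---|---|---|
| 1 per year | 28% | 45% | 57% | 74% |
| 3 per year | 20% | 58% | 72% | 85% |

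Here the time offset itself matters. Null rejection was 6–8% for the listed tests and 5–6% for the rate model.

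**The case against.** The strongest reply is that the protocol assigns no particular test to these outcomes. It nowhere dichotomises hypoglycaemia, and the choice of a count model for outcomes outside the main parameters may be left to a statistical analysis plan that is not at hand. That is fair as to detail. But the protocol does more than stay silent: it states what will be used for clinical outcomes, names a skew-appropriate model for costs only, and adopts a target (improvement) that Table 3 makes impossible for visits and hospitalisation.

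A reader might infer four stronger claims that the documents do not support.

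- *Every listed test ignores repeat events.* Only any/none tests do. A t or rank-sum test on counts, or on changes in counts, keeps them and ignores only time. A change-score t test is nearly as good as the adjusted rate model at 3 events per year (98% against 99%).
- *The trial's main safety comparison is blunted.* No outcome is labelled a safety endpoint, and hypoglycaemia sits under other outcome measures.
- *The listed tests seriously inflate false positives.* Null rejection reaches about 12% only if dropout is unequal and events are observed up to a continuous dropout date. On the questionnaire schedule the excess is small.
- *Event counts and dates are already in hand.* The protocol does not say that the questionnaire records either.

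Completers also share a nominal 12 months, so among them the offset is nearly constant. Visits may still be captured from case notes after a patient stops answering questionnaires.

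**Conclusion.** The point holds in a limited form. The named methods take no account of follow-up time, the any/none option discards repeats, and improvement is undefined for visits and hospitalisation. The last of these follows from the protocol alone and needs no assumption.

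Under the assumptions above, the baseline-adjusted rate model gains 13, 40 and 68 points of power over chi-square at 0.3, 1 and 3 events per year. Over rank-sum on counts it gains 10, 23 and 28 points, and over the change-score t test 21, 18 and 1. Over a t test on counts it gains 5, 13 and 15, mostly through the baseline count. The adjusted figures therefore apply to hypoglycaemia only. For visits and hospitalisation, which have no baseline, the gain over a t test on counts is small unless dropout differs between arms. Because the rate model's null rejection is 5–7%, a small part of its advantage may reflect test size.

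These are secondary outcomes and every event rate is assumed. The change is worth making, but it does not touch the sample size or the HbA1c comparison.

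**What to change.** In the Data Analysis section:

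- State for each event outcome whether it is analysed as a count or as any event.
- Analyse counts of minor hypoglycaemia and of DM-related visits and hospitalisations with a negative binomial or robust Poisson model. Use a log offset for the months covered by completed questionnaires or by records.
- Include the baseline hypoglycaemia count as a covariate.
- For visits and hospitalisation, compare follow-up counts rather than improvement. Model the two separately, since the Procedures section schedules regular pharmacist appointments in the collaborative arm.
- Report rate ratios with 95% confidence intervals.
- Keep Fisher's exact test for events too rare to model, such as major hypoglycaemia if few occur.

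The cost is mainly analysis wording. The model's fit must be checked, and the sponsor must confirm that the questionnaire records the number of events and the period covered. If it records only whether any event occurred, a count model is not available for hypoglycaemia, and the protocol should then say so.
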